6.1.4 Response Criteria

6.1.4.1 Evaluation of Target Lesions

Complete Response (CR): Disappearance of all target lesions, determined by two separate observations conducted not less than 4 weeks apart. There can be no appearance of new lesions.

Partial Response (PR): At least a 30% decrease in the sum of the longest diameter (LD) of target lesions, taking as reference the baseline sum LD. There can be no appearance of new lesions.

Progressive Disease (PD): At least a 20% increase in the sum of the LD of target lesions, taking as reference the smallest sum LD recorded since the treatment started, or the appearance of one or more new lesions.

Stable Disease (SD): Neither sufficient shrinkage to qualify for PR nor sufficient increase to qualify for PD, taking as reference the smallest sum LD since the treatment started.

6.1.4.2 Evaluation of Non-Target Lesions

Complete Response (CR): Disappearance of all non-target lesions and normalization of tumor marker level.

Incomplete Response/Stable Disease (SD): Persistence of one or more non-target lesion(s) and/or maintenance of tumor marker level above the normal limits.

Progressive Disease (PD): Appearance of one or more new lesions and/or unequivocal progression of existing non-target lesions

6.1.4.3 Evaluation of Best Overall Response

The best overall response is the best response recorded from the start of the treatment until disease progression/recurrence (taking as reference for progressive disease the smallest measurements recorded since the treatment started). The patient's best response assignment will depend on the achievement of both measurement and confirmation criteria.

Target Lesions	Non- Target Lesions	New Lesions	Overall Response	Best Response for this Category Also Requires:
CR	CR	No	CR	≥4 wks. confirmation
CR	Non- CR/Non- PD	No	PR	≥4 wks. confirmation
PR	Non-PD	No	PR	
SD	Non-PD	No	SD	documented at least once ≥4 wks. from baseline
PD	Any	Yes or No	PD	
Any	PD*	Yes or No	PD	no prior SD,
Any	Any	Yes	PD	PR or CR

^{*} In exceptional circumstances, unequivocal progression in non-target lesions may be accepted as disease progression.

Note: Patients with a global deterioration of health status requiring discontinuation of treatment without objective evidence of

disease progression at that time should be reported as "symptomatic deterioration". Every effort should be made to document the objective progression even after discontinuation of treatment.

For Patients with Non-Measurable Disease (i.e., Non-Target Disease)

Non-Target Lesions	New Lesions	Overall Response
CR	No	CR
Non-CR/non-PD	No	Non-CR/non-PD*
Not all evaluated	No	not evaluated
Unequivocal PD	Yes or No	PD
Any	Yes	PD

^{* &#}x27;Non-CR/non-PD' is preferred over 'stable disease' for non-target disease since SD is increasingly used as an endpoint for assessment of efficacy in some trials so to assign this category when no lesions can be measured is not advised

Note: If subjects respond to treatment and are able to have their disease resected, the patient's response will be assessed prior to the surgery.

6.1.5 Duration of Response

Duration of overall response: The duration of overall response is measured from the time measurement criteria are met for CR or PR (whichever is first recorded) until the first date that recurrent or progressive disease is objectively documented (taking as reference for progressive disease the smallest measurements recorded since the treatment started).

The duration of overall CR is measured from the time measurement criteria are first met for CR until the first date that recurrent disease is objectively documented.

Duration of stable disease: Stable disease is measured from the start of the treatment until the criteria for progression are met, taking as reference the smallest measurements recorded since the treatment started.

6.1.6 Progression-Free Survival

Progression-free survival (PFS) is defined as the duration of time from start of treatment to time of progression *or death, whichever occurs first.*

Progression is defined as death, radiographic progression as defined in 6.1.4.3, or clinical deterioration attributed to disease progression as judged by the investigator.

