 - Low dose low molecular weight heparins (LMWH) for prophylactic use are allowed if clinically indicated and the benefit outweighs the risk per the Investigator's discretion.
 - Therapeutic doses of LMWH or the direct factor Xa oral inhibitors rivaroxaban, edoxaban, or apixaban are allowed if clinically indicated (e.g., for the treatment of DVT), and the benefit outweighs the risk per the Investigator's discretion. See section 7.1.2 for management of thromboembolic complications while on study. See section 4.1.2.2 for prohibited anticoagulants. Accepted clinical guidelines regarding appropriate management while receiving any kind of anticoagulation therapy must be followed. This includes, but is not limited to, subject education regarding the potential adverse drug reactions, monitoring laboratory parameters, dose adjustments (e.g., due to kidney dysfunction). Caution is warranted in settings associated with an increased risk for bleeding such as gastrointestinal cancers, urothelial cancers, gastrointestinal mucosal abnormality (e.g., mucositis), renal or hepatic impairment, thrombocytopenia, arterial hypertension, or prior history of gastrointestinal bleed. For direct factor Xa inhibitors, the potential for drug-drug interaction with other concomitant medications, as well as gastrointestinal absorption, should be considered. Aspirin and other nonsteroidal anti-inflammatory drugs (NSAIDs) should not be used concomitantly with heparin or factor Xa inhibitors due to the increased risk for bleeding complications. The risks and benefits of the use of anticoagulants should be reassessed on a regular basis. For more information regarding the use of anticoagulants, refer to the prescribing information of the anticoagulant and accepted clinical practice guidelines.

4.1.2.2 Prohibited or Restricted Therapy:

The following therapies are prohibited until study treatment has been permanently discontinued:

- Any investigational agent or investigational medical device.
- Oral anticoagulation with coumarin agents (e.g., warfarin), direct thrombin inhibitors (e.g., dabigatran), direct factor Xa inhibitor betrixaban, platelet inhibitors (e.g., clopidogrel), and chronic use of aspirin above low dose levels for cardio-protection per local applicable guidelines), until 4 weeks after cabozantinib has been permanently discontinued.

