- Any non-protocol systemic anticancer treatment (e.g., chemotherapy, immunotherapy, radionuclides, drugs or herbal products used specifically for the treatment of the cancer under investigation).

- Immunosuppressive agents including immunosuppressive doses of systemic corticosteroids with exceptions as stated in Section 4.1.2.1.
- Live vaccines are prohibited while on study and until 5 months after last dose of IO
 agent (e.g., intranasal influenza, measles, mumps, rubella, oral polio, BCG, yellow
 fever, varicella, and TY21a typhoid vaccines). The use of inactivated (killed)
 vaccines for the prevention of infectious disease is permitted.
- Metamizole (dipyrone) because of its potential for causing agranulocytosis.

The following therapies should be avoided until study treatment has been permanently discontinued or until otherwise specified:

- Local anticancer treatment including palliative radiation, ablation, embolization, or surgery with impact on tumor lesions should not be performed until radiographic progression per RECIST 1.1 has been established.
- Erythropoietic stimulating agents (e.g., epoetin alfa and darbepoetin alfa) should not be used based on a report of increased risk of tumor recurrence/progression associated with erythropoietin (Wright et al 2007).
- Concomitant medications that are known to prolong the QTc interval should be avoided in subjects who receive cabozantinib until they have permanently discontinued cabozantinib treatment (refer to http://www.qtdrugs.org for a list of drugs which have the potential to prolong the QTc interval).
- Chronic co-administration of cabozantinib with strong inducers of the CYP3A4 family (e.g., phenytoin, carbamazepine, rifampin, rifabutin, rifapentine, phenobarbital, and St. John's Wort) may significantly decrease cabozantinib concentrations and should be avoided. Selection of alternate concomitant medications with no or minimal CYP3A4 enzyme induction potential is recommended.
- Caution must be used when discontinuing treatment with a strong CYP3A4 inducer in a subject who has been concurrently receiving a stable dose of cabozantinib, as this could significantly increase the exposure to cabozantinib.

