5.4 Follow-up Procedures

Patients will be followed every three months after completion of (or early withdrawal from) study treatment until death or up to 18 months after the last patient is enrolled, whichever comes first.

• Review of systems and determination of live status (either in clinic during standard visit or by phone)

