9.0 STATISTICAL CONSIDERATIONS

9.1 Study Design/Study Endpoints

This is a single-arm, open label, phase-II trial designed as a pilot to see if the treatment regimen is worthy of further study. Specifically, the trial is designed as the first stage of a Simon two-stage, minimax design[39]. The goal is to gather evidence on efficacy or futility of the study treatment in this study population, while monitoring toxicity. The two-stage approach offers economy and exposes the fewest possible participants to potential harm without substantial benefit, with control of the probability of errors in decisions.

Primary Endpoint: For efficacy the primary endpoint is progression-free survival at six months (PFS-6), dating from the first dose of study treatment. Progression is defined and determined as given in Section 61.6. For toxicity, the primary endpoint is the number of participants showing serious toxicity during their participation in the trial. Serious toxicities are given in Section 7.0.

Efficacy Null Hypothesis: Based on current outcomes for this study population[25][26], the null hypothesis is that 5% of evaluable patients will be progression-free at six months.

Efficacy Alternative Hypothesis: Based on our clinical judgment and aspirations, we anticipate that 20% (or more) of evaluable participants will be progression-free at six months. In our view, 20% progression-free at six months is the smallest advance that would be judged clinically worthwhile.

Secondary endpoints:

- Overall survival, defined as time from starting treatment to death from any cause.
- Objective response rate in patients with measurable disease as defined in section 6.0
- Safety as described in the adverse events in section 7.0

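### PFS-6 has no rule for another anticancer drug started before month 6 by a patient who stopped without progression; read literally, that patient counts as a success of the study regimen

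*Combined protocol and SAP*

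**What the plan says.** **Endpoint.** Section 6.1.6: "Progression-free survival (PFS) is defined as the duration of time from start of treatment to time of progression" or death, whichever is first. It then lists the events: "Progression is defined as death, radiographic progression as defined in 6.1.4.3, or clinical deterioration attributed to disease progression as judged by the investigator". Section 9.1 makes the primary endpoint "progression-free survival at six months (PFS-6), dating from the first dose of study treatment". Neither section, nor the analysis plan in 9.3, says how a new anticancer treatment before month 6 is handled.

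**Denominator.** Section 6.1.1 makes everyone who receives cycle 1 day 1 evaluable, and section 4.9 rules out replacement. An early stopper therefore stays in the count.

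**Stopping without progression.** Sections 4.6 and 5.6 allow treatment to end for adverse events, intercurrent illness, a hold of more than 28 days or the patient's decision.

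**Other therapy.** Section 4.1.2.2 introduces its list, which includes non-protocol systemic anticancer treatment, with "The following therapies are prohibited until study treatment has been permanently discontinued". Local treatment is in a separate list of things to avoid and "should not be performed until radiographic progression per RECIST 1.1 has been established". Section 6.1.4.3 nevertheless provides for resection: "If subjects respond to treatment and are able to have their disease resected", response is assessed before the surgery. It says nothing about PFS.

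**Data collected.** Concomitant medications are reviewed at the off-treatment visit, within 30 days of stopping (5.3.2, 5.5). The three-monthly follow-up consists of "Review of systems and determination of live status (either in clinic during standard visit or by phone"); the follow-up column in 5.5 has no medication entry.

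**The concern.** The trial has no control arm, so disease control produced by a later drug has nothing to be compared with and is credited to cabozantinib plus pembrolizumab. The decision rests on very small counts: at least 2 of 19 to go on, at least 4 of 27 to reject the null. One patient moved from failure to success can change either decision.

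The problem differs from a missing month-6 scan. Where a scan does exist, it confirms that the patient has not progressed and does not show which treatment was responsible. Without a record of later therapy, nobody could separate the two after the fact. Without a written rule, the choice would be made once the outcomes were known.

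**Working it through.** **Step 1. Reproduce the plan's design.** Inputs from section 9.2: null rate 0.05, alternative 0.20, stage one n = 19 (continue if at least 2), total n = 27 (reject if at least 4). Let X be the stage-one count, binomial (19, p), and Y the count in the next 8, binomial (8, p).

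- P(stop at stage one) = P(X ≤ 1). At p = 0.05: 0.3774 + 0.3774 = 0.755 (the plan states 0.75).
- P(reject) = P(X=2)·P(Y≥2) + P(X=3)·P(Y≥1) + P(X≥4). At p = 0.05: 0.1787 × 0.0572 + 0.0533 × 0.3366 + 0.0132 = 0.0102 + 0.0179 + 0.0132 = 0.041 (the plan allows 0.05).
- At p = 0.20 the same formula gives 0.803 (the plan states 80% power).

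The plan's figures are reproduced.

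**Step 2. How the text classifies the patient.** Take a patient who stops at month 2 for toxicity, starts another systemic drug and is alive without progression at month 6.

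- Non-evaluable would conflict with 6.1.1.
- Failure would need an event that 6.1.6 does not list.
- Censoring has no defined role in a fixed count of 2/19 or 4/27.
- Success fits 6.1.6 and 9.1 as worded.

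**Step 3. Size.** The documents give no frequency, so every input here is an assumption. Let d be the share who stop without progression before month 6, u the share of those who start another systemic drug, and s the share of those who are progression-free at month 6 only because of it. The apparent rate is 0.05 + c, with c = d × u × s.

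- For s, an exponential curve with median m gives 0.5^(t/m). The second-line median PFS values in section 1.1 include 2.1 months (ramucirumab alone) and 4.4 months (ramucirumab plus paclitaxel). At t = 6 months these give 0.5^(6/2.1) = 0.14 and 0.5^(6/4.4) = 0.39. At t = 4 months, m = 2.1 gives 0.27.
- Low: d = 0.10, u = 0.5, s = 0.14, so c = 0.007.
- Middle: d = 0.20, u = 0.5, s = 0.27, so c = 0.027.
- High: d = 0.20, u = 0.5, s = 0.40, so c = 0.04.

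| Added points c | Apparent rate | P(continue past 19) | P(reject 5%) |
|---|---|---|---|
| 0 | 5.0% | 0.245 | 0.041 |
| 0.7 | 5.7% | 0.296 | 0.062 |
| 2.7 | 7.7% | 0.436 | 0.143 |
| 3.7 (one patient in 27 on average) | 8.7% | 0.502 | 0.195 |
| 4.0 | 9.0% | 0.520 | 0.212 |

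**Step 4. Effect of the stricter count.** The sample size and cut-offs stay the same. If 5% and 20% are meant for the stricter endpoint, the error rate stays 0.041 and power 0.803. If the 20% target was meant to include patients helped by later therapy, the rate under the stricter count is lower: power is 0.757 at 18.75%, 0.703 at 17.5% and 0.576 at 15%.

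**The case against.** **The plan is silent; it does not state a rule.** No section says that these patients are successes, and counting whatever happens after a treatment switch is a legitimate choice. This stands as a limit on the wording. It does not remove the point, because the choice is not stated, and only success fits the text as it is.

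**Radiation and other local treatment.** A reader might infer that palliative radiation is exposed in the same way. The documents do not support that: section 4.1.2.2 says local treatment should wait for RECIST progression, which is already a PFS event. The open routes are systemic therapy after stopping, and resection of responders under 6.1.4.3.

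**Later therapy is never recorded.** That is also too strong. The off-treatment visit reviews medications, so a prompt switch can be captured. Only later starts are missed.

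**Month-6 status may be unknown.** Section 6.1.3 schedules scans until the end of treatment, 5.3.3 until the patient comes off study, and follow-up includes no imaging. Some early stoppers may therefore have no month-6 assessment, which is a separate problem. It reduces the number of patients affected here without closing the gap.

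**The pool may be small.** Section 4.2 allows each drug to be modified separately, and 5.6 lets some benefiting patients restart. This is fair, and it is why the size can only be shown as a range.

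**Conclusion.** The point holds in a limited form. On a literal reading of 6.1.6 and 9.1, a patient who stops without progression, takes another systemic anticancer drug and is progression-free at month 6 counts for the study regimen. Follow-up does not record such therapy if it starts after the off-treatment visit.

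With a true rate of 5% and an assumed 0.7 to 4 added percentage points, the probability of rejecting the null goes from 0.041 to about 0.06 to 0.21. This rests on the assumed stopping rate, 50% uptake, the exponential curve, and no affected patient being progression-free at month 6 without the other drug.

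A reader might infer a much larger effect. An added 2 to 8 points would give 0.11 to 0.46, but that needs every early stopper to switch, with the upper end close to the most favourable median above; nothing in the documents supports it.

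A reader might also infer that overall survival is wrong. It is death from any cause, so no death is misclassified; later therapy affects only its interpretation, and 9.3 plans no formal test of it.

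**What to change.** 1. In 6.1.6 and 9.1, state that a patient who starts non-protocol systemic anticancer therapy before six months without prior progression is counted as not progression-free in the primary PFS-6 count. Give the plain progression-or-death count as a sensitivity analysis.
2. In 5.4 and the follow-up column of 5.5, add subsequent anticancer therapy (type and start date), including radiation and resection, at the existing three-monthly contacts.
3. For resected responders, report PFS-6 both ways and say in advance which count drives the 2/19 and 4/27 decisions. Scoring them as failures penalises what may be the regimen's best result, so this is a real trade-off.
4. Reconcile 4.1.2.2 (surgery on tumour lesions before progression) with 6.1.4.3 (resection of responders).
5. State whether the 5% and 20% rates refer to the stricter count.

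**Cost.** A few sentences and one case report form field at contacts that already take place; no change to the sample size or cut-offs. PFS-6 may come out somewhat lower, and power falls below 0.80 if the 20% target was meant to include these patients (0.703 at 17.5%).

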6.2 Safety/tolerability

Analyses will be performed for all patients having received at least one dose of study drug. The study will use the CTCAE version 5.0 for reporting of non-hematologic adverse events (http://ctep.cancer.gov/reporting/ctc.html) and modified criteria for hematologic adverse events.

7.0 ADVERSE EVENTS

Adverse event (AE) monitoring and reporting is a routine part of every clinical trial. The following list of AEs (Section 7.1) and the characteristics of an observed AE (Section 7.2) will determine whether the event requires expedited (via AdEERS) reporting **in addition** to routine reporting.

7.1 Experimental Therapy

For the most recent safety update, please refer to the current Investigator's Brochure or Study Agent Prescribing Information.

7.1.1 Contraindications

Cabozantinib and pembrolizumab have no known contraindications.

7.1.2 Special Warnings and Precautions for Use *Cabozantinib*

Dermatologic toxicity: Palmar-plantar erythrodysesthesia syndrome (PPES) was commonly observed in clinical trials; severe PPES (≥ grade 3) also occurred. May require treatment interruption, dosage reduction, and/or discontinuation.

GI toxicity: Diarrhea was commonly observed in cabozantinib-treated patients in clinical trials. May require therapy interruption and/or dosage reduction. Cabozantinib is associated with a moderate emetic potential; antiemetics are recommended to prevent nausea/vomiting. [US Boxed Warning]: Cometriq: Serious GI perforations and fistulas have been reported when used for medullary thyroid cancer; discontinue for GI perforation or fistula formation. May be fatal. Tracheal/esophageal fistulas were also noted; some cases were fatal. GI fistula/perforation (including fatal perforations) were also reported in patients treated with cabozantinib. Monitor for signs/symptoms of perforations and fistulas, including abscess and sepsis. May require therapy discontinuation.

Hemorrhage: [US Boxed Warning]: Cometriq: Serious and occasionally fatal hemorrhage (including hemoptysis and gastrointestinal) has occurred with cabozantinib when used for medullary thyroid cancer. Monitor for signs/symptoms of bleeding and do not administer to patients with severe hemorrhage or a recent history of hemorrhage or hemoptysis. Severe hemorrhage has also been reported in patients with renal cell cancer and hepatocellular carcinoma, including grade 3 or higher events. Do not administer to patients who have a recent history of hemorrhage, including hemoptysis, hematemesis, or melena. Discontinue for grade 3 or 4 hemorrhagic events.

Hypertension: Treatment emergent hypertension was commonly seen in clinical trials (including grade 3 or higher toxicity and hypertensive crisis). Do not initiate cabozantinib in patients with uncontrolled hypertension. Monitor blood pressure prior to therapy initiation and regularly thereafter; withhold for hypertension that is

uncontrolled with appropriate medical management. May require cabozantinib dosage reduction and/or therapy discontinuation.

Infections and infestations: Infections are commonly observed in cancer subjects. Predisposing risk factor include a decreased immune status (e.g., after myelosuppressive anticancer therapies, splenectomy), destructive growth of the underlying malignancy including bone marrow infiltration with suppression of normal hematopoiesis, as well as the presence of IV devices. Infections and abscesses should be treated with appropriate local care and systemic therapy. Cabozantinib should be interrupted until complete healing has taken place.

Osteonecrosis of the jaw: Osteonecrosis has been reported in subjects treated with cabozantinib. Additional risk factors include use of bisphosphonates and denosumab, chemotherapy and anti-angiogenic drugs, use of corticosteroids, local radiotherapy, and dental or orofacial surgery procedures. Osteonecrosis of the jaw (ONJ) can manifest as jaw pain, osteomyelitis, osteitis, bone erosion, tooth or periodontal infection, toothache, gingival ulceration, or gingival erosion. Persistent pain or slow healing of the mouth or jaw after dental surgery may also be manifestations of osteonecrosis. Perform an oral examination prior to initiation of cabozantinib and periodically during cabozantinib treatment. Advise subjects regarding oral hygiene practice and to quickly report symptoms to Investigator. Caution should be used in subjects receiving bisphosphonates. Invasive dental procedures should be avoided. In cases where dental procedures are unavoidable, treatment with cabozantinib should be interrupted for at least 3 weeks prior to the procedure and resumed after complete wound healing has occurred. Bone healing may often require a protracted time. Withhold cabozantinib for development of ONJ until complete resolution.

Proteinuria: Proteinuria occurred in patients receiving cabozantinib in clinical trials; nephrotic syndrome was also reported (rare). Monitor urine protein regularly and discontinue therapy if nephrotic syndrome develops.

Reversible posterior leukoencephalopathy syndrome: Reversible posterior leukoencephalopathy syndrome (RPLS) has occurred with cabozantinib. Monitor for signs/symptoms of RPLS (seizures, headache, visual disturbances, confusion or altered mental function); if diagnosis confirmed, discontinue therapy.

Thromboembolic events: Thromboembolic events are frequent in cancer subjects due to procoagulant changes induced by the malignancy or anticancer therapy. DVT and pulmonary embolism have been observed in clinical studies with cabozantinib, including fatal events. Subjects who develop a pulmonary embolism and/or DVT should have study treatment interrupted until therapeutic anticoagulation is established. Treatment with cabozantinib may be resumed in subjects with pulmonary embolism or DVT if it is determined that the event is uncomplicated and that the subject is deriving clinical benefit from cabozantinib treatment and that anticoagulation does not place them at a significant risk that outweighs the benefit of resuming treatment per discretion of the Investigator and according to individual protocols. Therapeutic doses of LMWH or the direct factor Xa oral inhibitors rivaroxaban, edoxaban, or apixaban are allowed for management of thrombotic events. Other oral anticoagulants including coumarin agents (e.g., warfarin), direct thrombin inhibitors (e.g., dabigatran), direct factor Xa inhibitor betrixaban, platelet inhibitors (e.g., clopidogrel), and chronic use of aspirin above low dose levels for cardioprotection per local applicable guidelines are not allowed, until 4 weeks after cabozantinib has been permanently

discontinued. See Section 4.1.2 for additional restrictions on anticoagulation therapy.

Arterial thrombotic events (e.g., TIA, MI) have been observed in studies with cabozantinib. Subjects should be evaluated for pre-existing risk factors for arterial thrombotic events such as diabetes mellitus, hyperlipidemia, hypertension, coronary artery disease, history of tobacco use, and cardiac and/or thromboembolic events that occurred prior to initiation of study treatment. Further treatment with cabozantinib should be discontinued in subjects who develop an acute MI, cerebral infarction, or any other clinically significant arterial thromboembolic complication.

Wound healing impairment: Cabozantinib has the potential to cause wound healing complications and wound dehiscence which may even occur long after a wound has been considered healed. Therefore, surgical and traumatic wounds must not only be completely healed prior to starting cabozantinib treatment but must also be monitored for wound dehiscence, wound infection and other signs of impaired wound healing while the subject is being treated with cabozantinib. If dehiscence occurs, cabozantinib treatment should not be restarted until complete healing has taken place. Treatment with cabozantinib should be stopped at least 3 weeks prior to elective surgery. Do not administer cabozantinib for at least 2 weeks after major surgery and until complete wound healing.

Pembrolizumab

Dermatologic toxicity: Immune-mediated rashes, including Stevens-Johnson syndrome (SJS), toxic epidermal necrolysis (TEN, some fatal), exfoliative dermatitis, and bullous pemphigoid may occur with pembrolizumab. Monitor for suspected severe skin reactions and exclude other causes. Based on the severity of the dermatologic toxicity, withhold or permanently discontinue pembrolizumab and administer corticosteroids. Withhold pembrolizumab for signs/symptoms of SJS or TEN and refer for specialized care for assessment and management. Permanently discontinue pembrolizumab if SJS or TEN is confirmed.

Diabetes mellitus: Type 1 diabetes mellitus has occurred (including diabetic ketoacidosis). Monitor closely for hyperglycemia and other signs/symptoms of diabetes. Insulin therapy may be required; if severe hyperglycemia is observed, administer antihyperglycemics and withhold pembrolizumab treatment until glucose control has been accomplished.

Gastrointestinal toxicity: Immune-mediated colitis has occurred, including cases of grade 2 to 4 colitis. The median time to onset of colitis was 3.5 months (range: 10 days to 16.2 months) and the median duration was 1.3 months (range: 1 day to over 8 months). In many patients, colitis was managed with high-dose systemic corticosteroids for a median duration of 7 days (range: 1 day to 5.3 months), followed by a corticosteroid taper. Most patients with colitis experienced resolution. May require treatment interruption, systemic corticosteroid therapy, and/or permanent discontinuation. Monitor for signs and symptoms of colitis; administer systemic corticosteroids for grade 2 or higher colitis.

Hepatotoxicity: Immune-mediated hepatitis occurred (grades 2 to 4 hepatitis). The median onset for hepatitis was 1.3 months (range: 8 days to 21.4 months); the median duration was 1.8 months (range: 8 days to over 20 months). Hepatitis

resolved in most patients. Administer corticosteroids (prednisone 0.5 to 1 mg/kg/day [or equivalent] for grade 2 hepatitis, and prednisone 1 to 2 mg/kg/day [or equivalent] forgrade 3 or higher, each followed by a taper), and withhold or discontinue therapy based on the severity of liver enzyme elevations. Systemic corticosteroids were used to manage immune-mediated hepatitis in many patients; the median duration of high-dose corticosteroid therapy was 5 days (range: 1 to 26 days), followed by a taper. Monitor for liver function changes. May require treatment interruption, systemic corticosteroids (for grade 2 or higher toxicity), and/or permanent discontinuation. Pembrolizumab/axitinib combination therapy may result in higher frequencies of grades 3 and 4 ALT and AST elevations (compared to pembrolizumab monotherapy). The median time to onset of ALT elevation was 2.3 months (range: 7 days to ~20 months) for pembrolizumab/axitinib combination therapy, and over half of patients with ALT elevation required systemic corticosteroids; resolution of grades 2 to 4 ALT elevation occurred in most patients. When rechallenged with either pembrolizumab, axitinib, or both, over half of patients did not experience recurrence of ALT elevation to >3 times ULN. Monitor liver enzymes at baseline and then periodically during treatment; consider more frequent liver enzyme monitoring than for pembrolizumab (or axitinib) monotherapy. If liver enzymes are elevated, withhold pembrolizumab and axitinib, and consider corticosteroids as needed.

Hypersensitivity: Hypersensitivity and anaphylaxis have been observed (rare).

Hypophysitis: Immune-mediated hypophysitis occurred (grades 2, 3, and 4). The median time to onset was 3.7 months (range: 1 day to 12 months) and the median duration was 4.7 months (range: 8 days to over 12 months). Most cases were managed with systemic corticosteroids. Nearly half of patients with hypophysitis experienced resolution. Monitor for signs/symptoms of hypophysitis (eg, hypopituitarism, adrenal insufficiency). May require treatment interruption, systemic corticosteroids and hormone replacement therapy (as clinically indicated), and/or permanent discontinuation.

Infusion-related reactions: Infusion-related reactions (including severe and life-threatening cases) have occurred. Monitor for signs/symptoms of a reaction (eg, rigors, chills, wheezing, pruritus, flushing, rash, hypotension, hypoxemia, and fever). Interrupt infusion and permanently discontinue for severe (grade 3) or life-threatening (grade 4) infusion-related reactions.

Nephrotoxicity: Immune-mediated nephritis has occurred. The onset for autoimmune nephritis was 3.2 to 5.1 months (range: 12 days to 12.8 months) and the median duration was 3.3 months (range: 12 days to over 16 months). Grade 2 or higher nephritis should be managed with systemic corticosteroids (prednisone initial dose of 1 to 2 mg/kg/day [or equivalent], followed by a taper). Most patients required systemic corticosteroids. The median duration of corticosteroid use was 3 to 15 days (range: 1 day to 4 months), followed by a taper. Nephritis resolved in approximately one-third to one-half of affected patients. Monitor for renal function changes. May require treatment interruption, systemic corticosteroids (for grade 2 or higher toxicity), and/or permanent discontinuation.

Pulmonary toxicity: Immune-mediated pneumonitis has been observed, including grade 3, grade 4, and fatal cases. In patients with NSCLC, a higher incidence of pneumonitis was reported in patients who had received prior

thoracic radiation. The median time to development was 3.3 months (range: 2 days to ~19 months) and the median duration was 1.5 months (range: 1 day to over 17 months). Many patients required initial management with high-dose systemic corticosteroids; the median duration of initial corticosteroid therapy was 5 to 8 days (range: 1 day to ~10 months) followed by a corticosteroid taper. Pneumonitis resolved in half of the affected patients. May require treatment interruption, corticosteroid therapy (prednisone 1 to 2 mg/kg /day [or equivalent] followed by a taper, for grade 2 or higher pneumonitis), and/or permanent discontinuation. Monitor for signs and symptoms of pneumonitis; if pneumonitis is suspected, evaluate with radiographic imaging and administer systemic corticosteroids for grade 2 or higher pneumonitis. Pneumonitis occurred more frequently in patients with a history of prior thoracic radiation.

Thyroid disorders: Immune-mediated hyperthyroidism, hypothyroidism, and thyroiditis have occurred. The median onset for hyperthyroidism was 1.4 months (range: 1 day to ~22 months) and the median duration was 2.1 months (range: 3 days to over 15 months). Hyperthyroidism resolved in nearly three-fourths of affected patients. Hypothyroidism occurred with a median onset of 3.5 months (range: 1 day to 19 months) and median duration was not reached (range: 2 days to over 27 months). Hypothyroidism resolved in one-fifth of affected patients. The incidence of new or worsening hypothyroidism was higher in patients with squamous cell cancer of the head and neck. Monitor for changes in thyroid function (at baseline, periodically during treatment, and as clinically indicated) and for signs/symptoms of thyroid disorders. Administer thionamides and betablockers for hyperthyroidism as appropriate; may require treatment interruption and/or permanent discontinuation. Isolated hypothyroidism may be managed with replacement therapy. Thyroiditis occurred with a median onset of 1.2 months (range 0.5 to 3.5 months).

Other immune-mediated toxicities: Other clinically relevant immune-mediated disorders have been observed (may involve any organ system or tissue, and may be severe or fatal), including rash, exfoliative dermatitis, bullous pemphigoid, uveitis, arthritis, vasculitis, myositis, Guillain-Barré syndrome, pancreatitis, hemolytic anemia, sarcoidosis, serum sickness, myasthenia gravis, myelitis, myocarditis, and encephalitis. While immune-mediated toxicity generally occurs during treatment with pembrolizumab, adverse reactions may also develop after therapy discontinuation. If an immune-mediated adverse event is suspected, evaluate appropriately to confirm or exclude other causes: withhold treatment and administer systemic corticosteroids based on severity of reaction. Upon resolution to grade 0 or 1, initiate corticosteroid taper (continue tapering over at least 1 month). When reaction remains at grade 1 or less during taper may reinitiate pembrolizumab. Immune-mediated adverse reactions that do not resolve with systemic corticosteroids may be managed with other systemic immunosuppressants (based on limited data). Discontinue permanently for severe or grade 3 immune-mediated adverse event that is recurrent or lifethreatening.

